1 PROTOCOL SUMMARY

1.1 SYNOPSIS

Title:	Using Interactive Virtual Presence to Remotely Assist Parents with Child Restraint Installations
Study Background:	
Motor vehicle crashes are the third-leading cause of death to American children ages 1-5. When installed correctly, child restraints (car seats) reduce risk of serious injury and death. However, most restraints are installed incorrectly. The current gold standard for correct installation is systematic car seat checks, where certified technicians help parents, but car seat checks are highly underutilized due to barriers in access, scheduling, and resources.
 
The present study evaluates use of interactive virtual presence technology (interactive merged reality) – joint, simultaneous remote verbal and visual interaction and exposure to the same 3D stimuli – to assist remotely-located parents installing child restraints. If effective, this technology could supplement or replace in-person checks and revolutionize how government, industry, and non-profits help parents install child restraints properly.

Objectives:	This protocol describes a randomized non-inferiority trial to evaluate whether parents who install child restraints while communicating with remote expert technicians via interactive virtual presence on their smartphones achieve installations and learning not inferior in safety to parents who install restraints with on-site technicians.
Study Population:	Caregivers of children who have child restraints in a vehicle
Phase:	III
Description of Study Intervention:	Remote assistance with installation of child restraints in vehicles

2 INTRODUCTION

2.1 STUDY RATIONALE

Motor vehicle crashes are the third-leading cause of death for American children ages 1-5 years. Morbidity rates far exceed mortality and impact public health tremendously. In 2017, over 500 American children age 5 years and under were killed in motor vehicle crashes and over 37,000 others were injured seriously enough to visit an emergency department. Child restraints are documented to provide excellent protection to risk morbidity and mortality to children in motor vehicle crashes. However, child restraints are frequently installed incorrectly by caregivers. This study investigates the potential to use interactive virtual presence to remotely assist parents with installation of child restraints, offering a means to reach caregivers efficiently and broadly with valuable assistance to install child restraints correctly.

2.2 BACKGROUND

Child restraint systems

Child restraint systems (also called “restraints” and “car seats”) reduce risk of serious injury and death to infants and young children roughly threefold, but are most effective when installed correctly. Unfortunately, multiple studies suggest a large portion of child restraints are installed incorrectly. It is unclear exactly why child restraints are installed incorrectly with such frequency. One factor may be that manufacturer instruction manuals are difficult to comprehend or are not reviewed carefully by parents. Another explanation is the physical demands required to complete the task of installing a child restraint. Ergonomic research documents the fact that proper installation of child restraints requires some degree of strength and agility, especially if the installer is unfamiliar with optimal installation strategies. A third factor is that installation is simply very difficult. Correct installation often requires assistance from an expert.

Increasing the rate of correctly-installed child restraints

Individualized one-on-one installation of child restraints is considered the gold standard for child safety, but available evidence concerning incorrect installation rates and appointments at certified car-seat inspection stations and car seat checks (also called check-up events) suggest it is practiced infrequently.

There are several barriers to use of car seat checks. One is convenience. Many families with young children live busy, chaotic, and/or stressful lives and the task of obtaining, remembering, and attending an appointment for a car seat check may fall low in the list of household priorities. Another is access. Organizing and staffing car seat checks with certified technicians is expensive for government or non-profit agencies to administer. Demand greatly outpaces supply in most locations, and access is particularly poor in rural areas of the country. The present study will evaluate whether we might overcome barriers through use of mobile interactive virtual presence that permits remotely-located certified technicians to interact with parents to install child restraints in their vehicles at convenient times and places using a mobile smartphone.

Interactive virtual presence

Recent technological advances in interactive virtual presence – technology that integrates augmented and merged virtual reality to permit remote experts to train lay or professional individuals – suggests it

can be effective in a wide variety of tasks through joint exposure to 3D images and interactive simultaneous engagement with the object(s) of interest. For example, a remotely located machinist can help a laborer repair the electrical circuit on a complex piece of factory equipment without traveling on-site for repairs.

In technical language, interactive virtual presence refers to the opportunity for users to simultaneously engage in interactive visual, nonverbal and aural communication. It provides merged reality and concurrent virtual interaction. Users can instantly and simultaneously view and merge two real-time perspectives, offering opportunity for remote collaboration while interactively examining, pointing to, grasping, illustrating and discussing a video stream. Images can be frozen, drawn upon, animated, and viewed live. Interactive virtual presence can be delivered through a range of hardware platforms, including tablets and mobile smartphones.

In lay language, interactive virtual presence implies that users requiring help – in the case of our research, parents – may place their smartphone over a targeted area to allow the expert – in our case, a remotely-located certified technician – to “freeze” that image and then point to or grasp particular areas with their hands and/or with telestration tools like arrows and pointers located within the software while speaking. Thus, for example, if a parent was unsure where to connect a child restraint anchor, she could use her smartphone to show the technician the back seat of the car and request that the technician point with her finger to the location of the anchor. Similarly, a parent could direct his phone’s camera toward a child restraint to verify it is installed well and the technician might notice a loose strap, draw a circle around that strap, and request that the parent tighten it. Interactive virtual presence extends beyond traditional telemedicine and video chat, instead providing the opportunity to engage immersively in all tasks and activities that a live certified technician provides, but using technology from a remote location.

The cognitive and behavioral bases of child restraint installation

Installing a child restraint properly is a challenging task that requires complex cognitive processing and logical thinking, some degree of physical strength and dexterity, patience and persistence, and practice and training. Empirical research consistently demonstrates that parents are poor at the task when they engage in it without any resources or with only the manufacturer’s instruction manual.

The best alternative strategy to self-installation, and the recommendation of both pediatricians and traffic safety experts, is use of individualized instruction, education and assistance from a currently certified technician. Recent evidence from a study of 291 parents, some of whom had recently worked with certified technicians to install their restraint, showed that parents who worked with technicians had 90% fewer critical misuse errors than parents who had not worked with technicians. Interactions with technicians may also have some lasting effect over time. Among one sample of 47 parents, interaction with a certified technician yielded a significant drop in any misuse of the restraint upon a 4-month follow-up (from 80% to 66%), as well as a significant drop in “critical” misuse (from 52% to 40%).

2.3 RISK/BENEFIT ASSESSMENT

2.3.1 KNOWN POTENTIAL RISKS

Physical risk includes (a) minor risk of discomfort or injury while installing a child restraint and (b) minor risk of discomfort from heat while installing a car seat in an outdoor setting during hot weather.

Psychological risks include (a) embarrassment from engaging in the research protocol, which involves physical movement in the back seat of a vehicle, and (b) embarrassment to answer questionnaires that are mildly invasive, such as household income.

There is minimal social risk from participating in this study. The primary risk results from the possibility for a breach of confidentiality. No data we collect will be highly personal, but we will collect information that participants may wish to keep private (such as household income), and the risk of a confidentiality breach is a social risk.

Participants will use their own smartphone to participate in the study and in some cases may incur small costs to use their phone. There are no known legal risks involved in study participation.

2.3.2 KNOWN POTENTIAL BENEFITS

Study results may provide valuable information to reduce risk of child injury or death in motor vehicle crashes. Study participants will have their child restraints installed with assistance from certified technicians.

3 STUDY DESIGN

3.1 OVERALL DESIGN

A non-inferiority randomized controlled trial will be conducted.

4 STUDY POPULATION

4.1 INCLUSION CRITERIA

- Individuals who frequently drive children in their vehicles
- Live in broad geographic footprint of participating Safe Kids Worldwide data collection center: Safe Kids Alabama/Children's Health System (based in Birmingham, AL); Safe Kids California, Los Angeles/Los Angeles Children's Hospital (based in Los Angeles, CA); Safe Kids Charlotte/Mecklenburg/Carolinas Medical Center (based in Charlotte, NC); Safe Kids Oklahoma/The Children's Center Rehabilitation Hospital (based in Oklahoma City, OK); Safe Kids Greater Houston (based in Houston, TX); Safe Kids Vermont/University of Vermont Children's Hospital (based in Burlington, VT); and Safe Kids Lower Columbia/Cowlitz County EMS and Trauma Care Council (based in Kelso, WA)
- Access to smartphone or other internet-based device (e.g., tablet)

4.2 EXCLUSION CRITERIA

- Inability to communicate in English or Spanish
- Physical or mental disability that prohibits valid participation in the study

5 STUDY INTERVENTION

5.1 STUDY INTERVENTION(S) ADMINISTRATION

5.1.1 STUDY INTERVENTION DESCRIPTION

All visits will be conducted by two individuals, a researcher (who is also certified as a CPS technician) and a technician. Following baseline activities, the researcher will inform the participant of their random assignment to a condition, either installation with a certified technician via interactive virtual presence or installation via the traditional live technician interaction. In cases where there is more than one restraint in the vehicle, the researcher will use a random number generator to select one of the restraints as the target for the research.

Those parents randomly assigned to the interactive virtual presence condition will be instructed how to connect to the interactive virtual presence program using their personal smartphone. Participants will connect to the interactive virtual presence program, view a brief online instructional video on using it, and then connect remotely to a certified technician.

Ensuring ecological validity and pragmatic trial practice, the researcher and local technician will purposely “stay away” through the remote installation process, allowing the parent and remote technician to engage via interactive virtual presence to install the restraint correctly in the vehicle. Remote technicians will guide the interaction following standard Safe Kids Worldwide practice for live in-person installations and participants will physically install and adjust the restraint into their own vehicle.

Those parents assigned to the control condition, installation by a live technician, will engage in standard procedures at Safe Kids Worldwide car seat checks to install the target restraint into the vehicle. The live technician will not be the same individual as the researcher, although they will both be present at the same location during the research protocol.

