5.2 MEASURES TO MINIMIZE BIAS: RANDOMIZATION

Randomization lists will be generated by the study biostatistician and stored electronically. A separate randomization list will be generated for each site and all will utilize a randomly permuted block design to allow for balance among intervention arms as the research study progresses and to limit the ability of any research staff member from definitively knowing/predicting future assignment. Block sizes will range over all even numbers from 8 to 16 inclusive.

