7 STUDY ASSESSMENTS AND PROCEDURES

7.1 STUDY ASSESSMENTS

We will consider two primary outcomes, both derived from inspections of child restraint installations using objective coding sheets: (a) total number of inspection points that are correctly installed, translated into a percentage to account for different points for different (e.g., rear-facing vs forward-facing; seat belt vs LATCH) installations, and (b) dichotomous measure of whether the restraint was installed correctly vs. not correctly. Examples of inspection points include whether tether straps are twisted, whether the seat moves more than 1 inch to the left/right, whether seat belts are routed through the correct belt pathway, and whether the carrying handle is in the correct position.

Both outcomes will be collected at four time points: at baseline prior to any intervention, at post, immediately following the initial installation in both groups, at the start of the follow-up visit following 4 months of no active intervention by the research team, and at follow-up after parent installation without technician assistance.

We also will consider results from a brief knowledge questionnaire, which was adopted from an existing instrument. Secondary and covariate measures considered will include demographic traits of the participant (e.g., gender, race, ethnicity, SES, research site) and restraint (e.g., forward vs rear facing, LATCH vs seat belt installation), attitudes and beliefs about child restraints, perceived efficacy of the interventions, and reported behaviors using restraints.

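### No inspector is named and no masking is described, and under the visit procedure any on-site inspector would know the arm when scoring the post-installation inspection behind both primary outcomes

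*Combined protocol and SAP*

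**What the plan says.** Section 5.1.1 sets the staffing: "All visits will be conducted by two individuals, a researcher (who is also certified as a CPS technician) and a technician". It then sets when the arm becomes known: "Following baseline activities, the researcher will inform the participant of their random assignment to a condition". In the remote arm, "the researcher and local technician will purposely “stay away” through the remote installation process". In the control arm the on-site technician assists, and "The live technician will not be the same individual as the researcher, although they will both be present at the same location".

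Section 7.1 says that the two primary outcomes (the percentage of inspection points that are right, and whether the whole installation is right) are "both derived from inspections of child restraint installations using objective coding sheets". The first two inspections are made "at baseline prior to any intervention, at post, immediately following the initial installation in both groups". Two more take place at the follow-up visit after 4 months. One example of an inspection point is "whether the seat moves more than 1 inch to the left/right"; the other three concern twisted straps, the belt path and the position of the carrying handle.

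The section headed "5.2 MEASURES TO MINIMIZE BIAS: RANDOMIZATION" covers the site-specific lists and the permuted blocks. Under Aim 2 in section 8.3, an installation counts as correct on the dichotomous outcome only if every component is correct.

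No section says who carries out any of the inspections, or mentions masking, an independent assessor, or scoring from photographs or video.

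**The concern.** Participants cannot be masked in this trial, but the person who scores the seat could be. As the visit is written, the researcher announces the arm and the technician acts on it, so neither on-site person is masked by the time of the post inspection. Permuted blocks make the next assignment harder to predict; they do not hide the current one.

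The direction of any bias matters because this is a non-inferiority trial. Scoring that is lenient to the remote arm, or that levels the two arms, pushes the result towards non-inferiority, and a larger sample does not remove it. Scoring that is harsher on the remote arm costs power. The dichotomous outcome is exposed as well: where a seat has a single fault, one lenient call changes it from incorrect to correct.

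**Working it through.** **Who knows the arm at each inspection**

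- Baseline: made before the announcement, so not affected.
- Post: made after the announcement. The researcher has given the assignment. The technician has either assisted or kept away because of it. Both know the arm.
- The two follow-up inspections: section 5.1.1 puts two people at every visit, but the plan does not say whether they are the same two as at the first visit. Knowledge of the arm is possible but not established.

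**The plan's own figures**

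Inputs from section 8.2: SD 0.10, 664 per group, one-sided alpha 0.025 (z = 1.96), margin 0.025, attrition 10%.

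- SE of the difference = 0.10 × √(2/664) = 0.00549.
- Power = Φ((0.025 − d)/SE − 1.96), where d is the true deficit of the remote arm.
- d = 0: Φ(4.555 − 1.96) = 0.995. The plan states 99.5%.
- d = 0.010: Φ(2.733 − 1.96) = 0.780. The plan states 78%.
- Total: 664/0.90 = 737.8, rounded up to 738 per arm, or 1476. This matches.

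**Adding a scoring bias b (assumed)**

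If the true deficit equals the margin and scoring favours remote by b on average, the probability of wrongly declaring non-inferiority is Φ(b/SE − 1.96). If the arms are equal and scoring runs against remote by b, power is Φ((0.025 − b)/SE − 1.96).

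| b | b/SE | Error at the margin, bias towards remote | Power with equal arms, bias against remote |
|---|---|---|---|
| 0 | 0 | 0.025 | 0.995 |
| 0.0025 | 0.456 | 0.066 | 0.984 |
| 0.005 | 0.911 | 0.147 | 0.954 |
| 0.010 | 1.822 | 0.445 | 0.780 |

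Levelling fits the same formula: shrinking a true deficit of 0.025 by one fifth is b = 0.025/5 = 0.005.

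**What b means per seat**

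The documents do not give the number of inspection points, so this is also an assumption. With 20 points, one point is worth 0.05, and b = 0.005 is one favourable call in every 10 seats. With 40 points, one point is worth 0.025, and the same b is one call in every 5 seats.

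Section 8.2 sizes the trial on a difference in means only, so no matching calculation is offered for the dichotomous outcome.

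**The case against.** The plan does contain safeguards. The researcher is certified and is never the live technician, so the natural reading is that the researcher does the coding. Both staff keep away from the remote installation, the target restraint is chosen at random when there is more than one, and the scoring uses structured sheets. Three of the four example points are visible states that leave little room for interpretation. Section 10 says that other aspects are in the study's IRB protocol, which may name the inspector. Bias could also run against the remote arm, since the on-site staff are themselves in-person technicians; that would lower power and would not produce false non-inferiority.

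Much of this stands, and it rules out several stronger readings that a reader might infer:

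- That the inspection is unmasked as a matter of fact. The documents do not name the inspector, so this is an inference from the staffing.
- That live technicians score their own work. The documents do not say so; they only fail to exclude it.
- That randomization is the only protection against bias. The heading of section 5.2 suggests this, but the separation of roles and the coding sheets are protections too.
- That the 4-month inspections are compromised. Staffing at that visit is not stated.

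The objection does not remove the core point. If the researcher is the coder, that is the very person who announces the arm. Structured sheets limit discretion, but judging seat movement against a 1-inch limit is a hands-on call.

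**Conclusion.** The concern holds in limited form. Followed as written, section 5.1.1 gives both on-site staff knowledge of the arm before the post inspection, so any inspection by either of them would be made knowing it. The plan neither names another inspector nor keeps the assisting technician from coding.

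The size is illustrative. Over assumed net biases of 0.0025 to 0.010 towards remote, the error at the margin rises from 0.025 to between 0.066 and 0.445. The same biases against remote lower power at equal means from 0.995 to between 0.984 and 0.780. These figures rest on the plan's SD of 0.10 and 664 per group, and on bias values that the documents do not supply. A reader might infer that a false finding of non-inferiority is likely; the documents do not support that, because they establish neither the size nor the direction of any scoring bias. The case for a change is that the exposure is avoidable at small cost.

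**What to change.** **Section 5.1.1.** After baseline, the technician, not the researcher, reveals the assignment. In the remote arm the technician gives the connection instructions and then keeps away; parents still connect on their own phones. In the live arm the technician runs the session. In both arms the researcher stays out of sight of the vehicle until installation is finished. Only stepping away from the car is not enough, because the researcher could still see whether the technician is working there. The researcher then codes the post inspection alone, on a form that does not show the arm. The assisting technician never codes.

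**Section 7.1.** Name the inspector at each of the four time points and state whether that person is masked. At 4 months, someone who was not at the first visit codes where existing staffing already allows it; otherwise the researcher codes without access to the assignment. Ask parents not to say how they were helped, and record each case of unmasking.

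**Cost.** Protocol wording and a site instruction. The first visit uses the two people already present, and the follow-up rule asks for no one beyond existing staff. The sample size of 1476 and the stated power do not change. The downsides are that the researcher can no longer watch the session and that some unmasking by parents will remain.

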5.2 MEASURES TO MINIMIZE BIAS: RANDOMIZATION

Randomization lists will be generated by the study biostatistician and stored electronically. A separate randomization list will be generated for each site and all will utilize a randomly permuted block design to allow for balance among intervention arms as the research study progresses and to limit the ability of any research staff member from definitively knowing/predicting future assignment. Block sizes will range over all even numbers from 8 to 16 inclusive.

